Professor, School of Public Health and Family Medicine

Director, Centre for Infectious Disease Epidemiology and Research

University of Cape Town

Cape Town, South Africa

[name]

[contact]

[name]
Research Officer
School of Public Health & Family Medicine, Division of Epidemiology & Biostatistics
University of Cape Town
[name]
[contact]

[name], MPH
Associate Professor in Residence
Department of Obstetrics, Gynecology & Reproductive Sciences
University of California, San Francisco
ANSIRH Program, [name]
[name]
[contact]
[contact]

Study sponsor: National Institute of Mental Health (R34 MH118028)

ClinicalTrials.gov study number: NCT03836625

ABSTRACT

South Africa is home to the world's largest antiretroviral therapy (ART) program, but sustaining high engagement along the HIV care continuum has proven challenging in the country and throughout the wider region. Population mobility is common in South Africa, but important research gaps exist describing this mobility and its impact on engagement in HIV care. Postpartum women and their infants in South Africa are known to be at high risk of dropping out of HIV care after delivery and are frequently mobile. We recently developed a beta version of a smartphone application (app) – CareConekta – that detects a user's smartphone location to allow for prospective characterization of mobility. Through this three-year award, we propose to adapt and test CareConekta to conduct essential formative work on mobility and evaluate an intervention – the CareConekta app plus text notifications and phone calls and/or WhatsApp messages – to facilitate engagement in HIV care during times of mobility. During the three-year project period, our primary objective is to evaluate the acceptability, feasibility, and initial efficacy of using CareConekta as an intervention to improve engagement in HIV care. Our secondary objective is to characterize mobility among South African women during the peripartum period and its impact on engagement in HIV care. We will enroll 200 eligible women at the Gugulethu Midwife Obstetric Unit in Cape Town, South Africa. This work will provide critical information about mobility during the peripartum period and the impact on engagement in HIV care, and piloting an intervention to improve engagement. This study will lay the necessary groundwork for a larger efficacy trial of the intervention within different geographic settings.

INTRODUCTION

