With more than seven million HIV-infected people,¹ South Africa is home to more people living with HIV than any other country in the world,² and their national ART program is the world's largest.² South Africa adopted a "treat all" policy to provide ART to all HIV-positive people, regardless of CD4+ cell count, in September 2016.³ Expanded ART availability has dramatically altered the health and quality of life of people living with HIV/AIDS, with an estimated life expectancy gain of 11.3 years between 2003 and 2011 due to ART⁴ and a 77% decrease in HIV transmission in stable serodiscordant couples.⁵ However, the rapid scale-up of the national ART program has put tremendous pressure on the limited resources of a public health sector that is hurrying to meet this immense need, and despite widespread availability of ART, over 135,000 people died of AIDS-related causes in 2016 in South Africa.¹ HIV and tuberculosis (usually exacerbated by HIV) are the top two causes of death among women ages 15-44 in South Africa.⁶ The potential for improved health through expanded ART availability will only be realized if individuals sustain engagement in HIV care.

Black African women of reproductive age (ages 20-34) are the population most heavily affected by the South African HIV epidemic, with 31.6% prevalence.⁷ Access to ART for all HIV-positive pregnant women through Option B+ has helped to reduce mother-to-child transmission of HIV to the point where near-elimination is now thought possible.⁸ Despite this astounding achievement, there is mounting evidence that women who initiate ART during pregnancy may be at very high risk of loss to follow-up (LTFU),⁹⁻¹² with re-engagement in routine HIV care after delivery a particular concern.^{13,14} The problem of patient LTFU within the public sector in South Africa has been well documented.^{15,16} Our earlier research conducted in South Africa found that 25.2% of women pregnant at ART initiation were LTFU after one year, compared to 15.8% of men and 11.1% of non-pregnant women.¹⁰ Our work also has helped to pinpoint the timing of LTFU to after delivery: among women diagnosed with HIV during antenatal care in Johannesburg, 47.9% were lost within six months of delivery;¹³ in Cape Town, disengagement was over twice as frequent in the postpartum period as during antenatal care.¹⁷

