A challenge to ensuring a continuity of HIV care is that the fragmented health care system is not adapted for a mobile population. Patients considered LTFU actually may have switched facilities on

their own as “silent transfers,” which typically are not recognized due to unlinked data across facilities.^{18–20} This misclassification makes it very difficult to accurately assess the effectiveness of national ART programs. Mobility as a potential barrier to engagement in HIV care has been noted in Kenya,^{21,22} Lesotho,²³ Zambia,²⁴ and the US²⁵. South Africa’s population is highly mobile; the most typical pattern is of circular, within-border migration between rural and urban areas, with the mobile individual keeping strong ties to the rural areas by sending remittances to their family and returning to the rural area for holidays and family events, and upon retirement, illness, or during lapses in employment.²⁶ Postpartum women in South Africa are likely to be a particularly mobile group, due to a tradition of returning to one’s rural home after delivery to receive care from family members.^{12,27,28} Our recent formative work at three sites in Johannesburg found that among 150 peripartum, HIV-positive women interviewed, 44% planned to travel around delivery – typically after delivery – to stay with family, sometimes leaving the infant in the care of family while the mother returned to work in Johannesburg (manuscript under review). HIV-exposed infants – even if HIV-uninfected – are at higher risk of mortality than HIV-unexposed infants²⁹ and require attentive follow-up. With no way of tracking mobility, it is difficult to intervene appropriately to ensure continuity of HIV care for mother and infant.

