For a more detailed assessment of mobility, we will use ArcMap to geographically place all locations in which participants were recorded during the study period. We will plot origin and destination locations on a map of South Africa, and neighboring countries (if necessary). We will connect origin and destination locations using ArcMap's XY-to-line tool, and will use a spherical calculator to estimate the distance between origin and destination. The geographic data will be used in conjunction with the novel metrics of mobility developed by [name], which are reflective of the complex forms of mobility in sub-Saharan Africa. For example, we will apply geopolitical boundaries to location codes so that measures of internal migration and localized mobility within and across those boundaries can be estimated, such as inter- and intra-provincial mobility. We also will map mobility flow according to origin and destination pairs, classified by geopolitical categories. We will thereby demonstrate how geographic data can be used to characterize the mobility of populations – providing a vital alternative to survey measures – in order to measure the impacts of that mobility on care cascade outcomes, with broad applicability to the measurement of its impact on other health outcomes. We also will conduct a secondary analysis to validate whether self-reported anticipated travel matches data collected from the CareConekta app.

Aim 1b. To assess the association between mobility and engagement in HIV care for mother (retention in care and viral suppression six months after delivery) and infant (completion of routine early infant diagnosis).

Outcome: Impact of mobility on engagement in HIV care in the absence of the intervention
We will limit the analysis to the control arm only to explore the impact of mobility on engagement in HIV care in the absence of intervention. We will report baseline participant characteristics as collected on the questionnaire. We will report proportions and 95% confidence intervals for categorical variables and medians and interquartile ranges for continuous variables. Open-ended questions will be reviewed for key themes. Themes will be abstracted and quantified.

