To assess engagement in HIV care, we will report retention in care, which will be assessed at the six-month postpartum point and defined as no documented HIV-specific contact with any healthcare facility (including medication pick-ups) for >3 months. We also will report viral suppression six months after delivery, using thresholds of ≤ 50 and ≤ 1000 copies/ml. Additionally, we will report vertical HIV transmission and completion of the routine 10-week infant PCR test.

We will fit a series of models of mobility metrics on outcomes. For one, we will use a dichotomous exposure of mobility (any travel >50 km: yes/no), we will use Cox proportional hazard regression models to estimate the association of mobility on these outcomes, and will produce adjusted hazard ratios and 95% confidence intervals for retention in care and achieving viral suppression. We also will identify other predictors of engagement in HIV care. We will produce crude Kaplan-Meier curves to time to loss to follow-up and time to viral suppression by mobility group. Additionally, we will perform sensitivity analyses to explore how the estimated effect size changes when using varying cut-off points to define mobility.

Aim 2a. To assess the acceptability and feasibility of the standard and enhanced app, with a focus on identifying user preference and implementation outcomes.

Outcome: Acceptability and feasibility of CareConekta

Acceptability and feasibility data will be collected among all 200 participants. Those in the intervention arm will receive additional questions related to the enhanced app features. The outcomes selected for analysis in Aim 3a correspond with the Technology Acceptance Model for Resource-Limited Settings (TAM-RLS) framework, which was designed to draw attention to end-user acceptability as a predictor of mHealth technology adoption in low-resource settings.⁴⁶ We will report proportions and 95% confidence intervals for categorical variables and medians and interquartile ranges for continuous variables. For open-ended questions, we will create a list of categorical themes that emerge over multiple readings and calculate the proportions for the response categories. We will select key illustrative quotes for each theme.

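### Aim 1b uses an ever/never travel label in a Cox model and Kaplan-Meier curves without a time zero, exposure start date or loss date, so its hazard ratio for loss to follow-up can mislead

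*Combined protocol and SAP*

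**What the plan says.** In Analysis Plan and Study Outcomes, Aim 1b is restricted to one arm ("We will limit the analysis to the control arm only"). It announces a series of models and describes one: "we will use a dichotomous exposure of mobility (any travel >50 km: yes/no), we will use Cox proportional hazard regression models". Retention is assessed at six months postpartum and is "defined as no documented HIV-specific contact with any healthcare facility (including medication pick-ups) for >3 months", wording that in fact describes loss. The plan continues: "We will produce crude Kaplan-Meier curves to time to loss to follow-up and time to viral suppression by mobility group". The sensitivity analyses it names are "sensitivity analyses to explore how the estimated effect size changes when using varying cut-off points to define mobility".

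Aim 1b gives no time origin, no date or window for travel, and no rule for dating a loss. It names a distance only, whereas Aim 1a also requires more than 7 days away and counts travel over the whole study period. Follow-up is about nine months (Selection of study participants). Location points carry timestamps (Mobility data), so the dates will exist, but Aim 1b does not say how they enter the model.

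**The concern.** At each loss, a Cox model compares the women then at risk. If the label reflects travel at any time, a woman who travels in month 7 already sits in the travel group in month 1, and her care before the trip counts as travel time. That period may be long. In the formative work cited in the Introduction, "44% planned to travel around delivery – typically after delivery".

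The outcome adds to this. If loss is dated at last contact, a gap of more than three months seen at six months postpartum must begin by about three months postpartum. Trips may count until follow-up ends, so some come after any countable loss could have begun.

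The Abstract states the stake: "Our secondary objective is to characterize mobility among South African women during the peripartum period and its impact on engagement in HIV care". A hazard ratio (HR) pulled toward 1 could be read as mobility mattering little for retention, and the confidence interval would not reflect the timing error. With no dating rule, the HR also depends on a choice that could be made after the data are seen.

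**Working it through.** **1. The plan's own figures.** Sample Size expects 25% of 200 to travel: 200 × 0.25 = 50, as stated. If that share holds in the control arm, 100 × 0.25 = 25 travellers. No event or power figure is given for Aim 1b.

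**2. Dilution by hand and by simulation.** Assumptions: enrolment at month 0, delivery at month 3, six months postpartum at month 9; constant loss hazard from enrolment or from delivery; first trip uniform over months 0-9, 3-9 or 3-5; true HR 2.0 from the trip onward; all travel recorded; loss does not prompt travel. Loss is 25% (assumed) or 47.9% (Introduction, Johannesburg: "47.9% were lost within six months of delivery").

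Ignoring depletion, the ever/never HR is about 1 + (2 − 1) × f, where f is the share of a traveller's countable time at risk that falls after her trip. With countable loss ending at month 6:

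| Loss from | Trips (months) | Mean post-trip time / time at risk | By hand | Simulated, 25% lost | Simulated, 47.9% lost |
|---|---|---|---|---|---|
| month 0 | 0-9 | (18/9)/6 = 0.33 | 1.33 | 1.28 | 1.27 |
| month 0 | 3-9 | (4.5/6)/6 = 0.125 | 1.13 | 1.12 | 1.10 |
| month 0 | 3-5 | (6 − 4)/6 = 0.33 | 1.33 | 1.28 | 1.26 |
| month 3 | 0-9 | (1.0 + 0.5)/3 = 0.50 | 1.50 | 1.48 | 1.41 |
| month 3 | 3-9 | (4.5/6)/3 = 0.25 | 1.25 | 1.21 | 1.19 |
| month 3 | 3-5 | (6 − 4)/3 = 0.67 | 1.67 | 1.63 | 1.59 |

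The simulations use 300,000 women per scenario. They run slightly below the hand values because exposed women leave the risk set sooner and the Cox estimate averages on the log scale. A true 1.0 reads 0.99-1.01. With 44% travelling, a true 2.0 reads 1.09-1.64. Time-updated exposure with exact loss dates returns 1.97-2.02 for a true 2.0 and 0.99-1.02 for a true 1.0.

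If loss may begin up to month 9, ever/never reads 1.25-1.82. On the log scale the dilution is ln(2/1.63) = 0.20 to ln(2/1.10) = 0.60 in the first case, and ln(2/1.82) = 0.09 to ln(2/1.25) = 0.47 in the second: 0.09-0.60 overall.

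**3. When the conditions fail (countable loss to month 6, ever/never model).**
- Half of post-loss travel unseen: a true 2.0 reads 0.62-1.38. All of it unseen: 0.19-1.15.
- Loss doubles later travel and it is seen: a true 1.0 reads 1.40-1.94, a true 2.0 reads 1.86-2.11.
- 10-20% of travellers still in care are coded lost: a true 1.0 reads 1.07-1.79. This can happen because facility and dispensing data cover the Western Cape only (File review activities).

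**4. The loss date (visits every 1, 2 or 3 months).**

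| Case | Ever/never | Time-updated, last contact | Time-updated, next contact due | Time-updated, end of gap |
|---|---|---|---|---|
| True 2.0 from the trip onward | 1.14-1.81 | 1.71-1.96 | 1.94-2.06 | 1.37-2.02 |
| Trip affects only the next due visit | 1.07-1.31 | 0.88-0.99 | 1.30-1.77 | 1.17-1.77 |
| True 1.0, 10-20% of travellers miscoded as lost | 1.07-1.79 | 0.93-1.19 | 1.20-3.60 | 1.12-2.80 |

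No single dating is safe in all three rows.

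**5. Precision per 100 women.** For ever/never, SE ≈ 1/√(d × 0.25 × 0.75): 0.46 for 25 losses and 0.33 for 47.9. The simulated scenarios give about 0.30-0.45. Time-updated, roughly 1-12 losses fall in exposed time and the SE is about 0.34-0.94.

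**The case against.** Aim 1b is exploratory, with perhaps 25 travellers, and sampling error is large whichever model is used. In 3 of the 12 scenarios of step 2, ever/never has the lower root-mean-square error (0.74 v 0.94, 0.69 v 0.74, 0.59 v 0.64). The plan never says the label is fixed, and the model described is one of a series. It speaks of association. If mobility marks a kind of woman, with HR 2.0 from time zero, ever/never reads 1.97-2.03 and time-updated 1.68-1.97. All of this stands. It argues for adding the time-updated analysis and stating which effect is wanted, not for leaving the dates unstated. No other model in the series is described, and the named sensitivity analyses do not address timing.

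A reader might infer more, in three ways:
- **That the trial will understate the harm of travel.** The documents do not settle this. Travel after loss that goes unseen lowers the HR. Travel prompted by loss, or care outside the Western Cape read as loss, raises it.
- **That the model will make travel look protective.** With all travel recorded, a true 1.0 is unbiased. The lowest figures need post-loss travel to go unseen, yet location is collected through the app throughout follow-up, independently of clinic attendance, and lost women are traced.
- **That a time-updated model with loss dated at last contact should simply replace the plan.** Step 4 shows that this can hide a harm which ever/never at least shows in the right direction.

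**Conclusion.** The omission is real: Aim 1b names no time zero, exposure start or loss date, and its natural reading is one label per woman. For loss to follow-up, three conditions together (travel acts only from the trip onward, loss does not prompt travel, all travel is recorded) mean that a true HR of 2.0 reads about 1.1-1.6 if countable loss begins by three months postpartum, or about 1.25-1.8 if it may begin up to six months. The wider window cannot be excluded, because files of women who do not return are reviewed at least seven months after estimated delivery.

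The sizes rest on assumed travel timing and loss rates, which the documents do not give for this site. Viral suppression was not examined. The randomised Aim 2b comparison is unaffected. This should be corrected because Aim 1b serves the secondary objective and the pilot is meant to prepare a larger trial.

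**What to change.** - **(a)** State time zero, the travel window and the rule for dating loss.
- **(b)** Add a time-updated mobility analysis: unexposed until the travel definition is first met, exposed after, from the time-stamped GPS data. Base any statement about the effect of travel on loss on it, and keep ever/never as a descriptive association.
- **(c)** Report the time-updated HR with loss dated at last contact, at the date the next contact was due, and at the end of the three-month gap. Do not make last contact the sole primary choice, and say if conclusions differ.
- **(d)** Alongside the two later datings, always show a sensitivity analysis that counts NHLS tests from any South African facility and self-reported clinic switching as contact. This is a partial remedy: NHLS holds laboratory records, not visits or dispensing.
- **(e)** Label the ever/never Kaplan-Meier curves descriptive, or use Simon-Makuch-type curves.
- **(f)** Report the number of losses in exposed time beside each HR.

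The cost is SAP wording, a counting-process dataset and a few extra runs, with no new data collection. Trips known only from self-report may lack exact dates. The main price is precision: with so few losses in exposed time, the time-updated estimate will have a wide interval and should be reported as such.

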In 2017, through a small grant from the Tennessee Center for AIDS Research (TN CFAR), we conducted formative research on smartphone use among our target population: peripartum, HIV-positive women at the proposed study site. Through focus group discussions (Vanderbilt IRB approval: 161805; UCT HREC approval: 792/2016), respondents told us they had few issues with data connectivity and privacy while using smartphones, and they were highly enthusiastic about mHealth interventions.⁴⁰ We also identified that over half of HIV-positive pregnant women we sampled owned a smartphone, the WhatsApp messaging app is very popular and widely-used, and about 90% of phones used the Android operating system.⁴⁰ We specifically asked participants about tracking their mobility for research purposes, and acceptability was high, noting that clinics could use an individual’s location to help them find a new facility when traveling.

Based on this formative information, and through the same TN CFAR pilot funding, we developed a beta version of the app that we will now adapt and pilot: CareConekta. This smartphone app uses

the phone's GPS to prospectively characterize mobility and intervene in real-time. The beta version app was developed in collaboration between the current study team ([name], [name], [name]) and [name] of Vanderbilt University Medical Center's Department of Biomedical Informatics.

STUDY AIMS

Aim 1: Characterize mobility among South African women during the peripartum period and its impact on engagement in HIV care.

Aim 1a. To use GPS location data from CareConekta and spatial analysis to characterize peripartum mobility within the complete observational cohort (n=200), including the frequency, distance, and timing.

Aim 1b. To assess the association between mobility and engagement in HIV care for mother (retention in care and viral suppression six months after delivery) and infant (completion of routine early infant diagnosis).

Aim 2: Evaluate enhanced CareConekta as an intervention to improve engagement in HIV care.

Aim 2a. To assess the acceptability and feasibility of the standard and enhanced app, with a focus on identifying user preference and implementation outcomes.

Aim 2b. To evaluate the initial efficacy of the enhanced CareConekta intervention, using notifications and staff contact to improve engagement in HIV care, by assessing the association between study arm and engagement in HIV care at six-months postpartum.

STUDY DESIGN

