Electronic and paper files will be reviewed after the participant's final visit to assess engagement in HIV care. If the participant fails to return for a final visit, files will be reviewed a minimum of seven months after estimated delivery. Electronic data on health facility visits and pharmacy dispensing, including facility recorded deaths, will be requested the Provincial Health Data Centre of the Western Cape Department of Health by providing a list of folder numbers of women who have consented and enrolled in the study. These data include all public health facilities in the Western Cape Province, which is the location of the study site. Laboratory records, including viral loads, from any South African facility will be abstracted from the NHLS database. Participants in both arms who are lost from the study at the time of study close will be traced through staff outreach and electronic/paper medical records. Informed consent will include permission to link with electronic medical records.

Table of schedule of measures

Item for completion	Enrolment	Early postpartum phone call	6 months postpartum
Eligibility Checklist	x		
Informed Consent	x		
Linkage form	x	x child details	
Randomisation log	x		
Demographics and medical history	x		x
Maternal mobility (past and planned)	x		x
Maternal clinic switching	x		x
Perceived barriers and facilitators of engagement in care	x		x
Depression (PHQ-4)	x		x
Alcohol and drug use (AUDIT-C and DUDIT Q1)	x		x
Patient provider relationship scale	x		x
ART adherence	x		x
WHO VAW (intimate partner violence)	x		
Social impact scale (stigma)	x		
Availability of social support	x		
Life events (trauma)			x
Infant health			x
Child mobility			x
Acceptability of CareConekta			x
Impact of COVID-19 & lockdown of HIV care and mobility			x
Laboratory tests			
HIV viral load*			x
Record review			
Antenatal and obstetric information	x	x	x
ART pharmacy records	x	x	x
Maternal laboratory results	x	x	x
Child HIV testing		x	x

* If no routine viral load result found in the three months before the study visit

DATA COLLECTION AND STORAGE

Data collection methods

Data will be collected in three ways:

- Face-to-face enrollment and follow-up questionnaires

- Medical record review (electronic and paper file records) to determine participant engagement in HIV care
- Electronic app usage and mobility data

Questionnaire data

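### Aim 1b sets no time window on maternal travel for the 10-week infant PCR outcome, so travel after the test was due counts as exposure

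*Combined protocol and SAP*

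**What the plan says.** The Aim 1b objective covers mother "and infant (completion of routine early infant diagnosis"). The Aim 1b analysis text measures this as "completion of the routine 10-week infant PCR test" and restricts the analysis to the control arm.

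On exposure, it says "We will fit a series of models of mobility metrics on outcomes" and then spells out one of them: "we will use a dichotomous exposure of mobility (any travel >50 km: yes/no"). Cox models are to relate this to the outcomes just listed. Hazard ratios are named only for maternal retention and viral suppression, and Kaplan-Meier curves only for time to loss to follow-up and time to suppression. The planned sensitivity analysis varies the cut-off that defines mobility and does not mention timing.

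Aim 1a counts travellers over the whole study period. It relates travel to delivery date, but only descriptively. The app stays on the phone until the six-month postpartum visit.

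The Table of schedule of measures lists "Child mobility" at six months. No analysis is stated for it. The Introduction reports that mothers in the formative work travelled around delivery, "sometimes leaving the infant in the care of family while the mother returned to work in Johannesburg".

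**The concern.** The infant outcome is settled at about 10 weeks of age, while the stated exposure can accrue until about 26 weeks. A mother who first travels in month 4 would be classed as mobile although her infant's test was due weeks before. That trip cannot have caused a missed test. Mixing such women with those who travelled before the test pulls the two mobility groups together.

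At stake is the one infant question in Aim 1b. A diluted estimate from a small control-arm sample could be read as showing that mobility has little bearing on early infant diagnosis, and could mislead the design of the larger study this pilot is meant to inform.

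**Working it through.** **The plan's own figure.** The Sample Size section expects 25% of participants to travel long distance: 0.25 × 200 = 50, as stated. Aim 1b uses the control arm only (n = 100), so about 0.25 × 100 = 25 travellers are expected there.

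**Inputs.**
- From the documents: enrolment from 28 weeks' gestation; follow-up to six months postpartum; PCR at 10 weeks; 25% travelling.
- Assumed: delivery at 40 weeks; six months = 26 weeks; first trips spread evenly over the period; women who first travel after week 10 complete the test at the same rate as non-travellers.

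**Share of follow-up after week 10.** The formula is (26 − 10) / (weeks from enrolment to delivery + 26).
- Enrolment at 28 weeks: 16/(12 + 26) = 16/38 = 42%
- Enrolment at 32 weeks: 16/(8 + 26) = 16/34 = 47%
- Enrolment at 36 weeks: 16/(4 + 26) = 16/30 = 53%
- All travel postpartum: 16/26 = 62%

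**Women classed as mobile on later travel only.** 25 × 16/38 = 10.5 to 25 × 16/26 = 15.4, or about 10-15 of 25.

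**Dilution.** If a share m of travellers first travel after week 10, the observed risk difference is (1 − m) times the true one. This leaves 1 − 0.42 = 58% down to 1 − 0.62 = 38%. A true difference of 20 percentage points (assumed) would appear as 20 × 0.58 = 11.6 down to 20 × 0.38 = 7.6 points.

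**Sensitivity to the even-spread assumption.**
- Trips clustered early, for example m = 20%: 25 × 0.20 = 5 women misclassified, and 20 points becomes 20 × 0.80 = 16.
- Two independent trips per woman: both must fall after week 10, so m becomes 0.42² = 0.18 to 0.62² = 0.38. That is 25 × 0.18 = 4.5 to 25 × 0.38 = 9.5 women, with 82% to 62% of the difference kept.

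**Precision with and without a window.** Assume completion of 90% in non-travellers and 70% in travellers, two-sided 0.05, and m of 42% to 62%. Approximate power is 0.35 down to 0.20 with the unwindowed variable (25 exposed). It is 0.55 down to 0.47 with exposure limited to travel before week 10 (about 15 down to 10 exposed). The window helps despite the smaller exposed group, but neither version is well powered.

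**The case against.** The strongest reply is that the plan never says infant completion will be related to travel over all of follow-up. That is inferred from the missing window and from the Aim 1a definition. The quoted exposure is one of a series of models, the others undefined, and the infant PCR reaches the Cox model only through a general reference to the listed outcomes. This stands as a limit on certainty. It does not remove the gap: no infant-specific exposure or effect measure is given, and the only exposure spelled out has the timing problem.

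The size is also open to challenge. The Introduction describes planned travel around delivery, typically after it, and Aim 1a allows for several trips. Both make the share first travelling after week 10 smaller than an even spread gives. This stands, and the even-spread range should not be read as an estimate.

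Aim 1b is exploratory and sits in a pilot with no formal sample size calculation. That limits the consequences but is no reason to leave the exposure undefined.

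Two stronger readings are tempting. A reader might infer that the mother's travel is the wrong person's exposure, since mother and infant may live apart. The documents do not support this. Aim 1 is to "Characterize mobility among South African women during the peripartum period and its impact on engagement in HIV care", so maternal mobility is the intended exposure. Infant location is a further question, and no separation rate is given. A reader might also infer that the infant objective cannot be answered. That fails too, because the plan collects time-stamped coordinates, infant date of birth and child HIV testing records.

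**Conclusion.** The concern holds as a gap in the analysis text. Followed as written, Aim 1b counts maternal travel after the 10-week test was due as exposure for an outcome already fixed, and no stated analysis corrects this. The expected direction is towards no association.

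The documents do not fix the size. With evenly spread first trips, 42-62% of travellers, about 10-15 of 25 control-arm women, would be exposed only after week 10, and 38-58% of a true difference would remain. With early clustering or repeated trips the loss is smaller. These figures also rest on the plan's 25% travel estimate and on late travellers completing the test at the non-travellers' rate. The problem lies in the wording of the analysis, not in the data collected.

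**What to change.** For the infant PCR outcome, state in Aim 1b:

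1. Exposure is maternal travel that starts before one fixed time point, the same for every infant whether tested or not, for example from enrolment or birth to the 10-week due date.
2. Completion is analysed as a binary outcome, not by Cox regression.
3. Maternal mobility stays the main exposure, as Aim 1 states. The child-mobility items are used only in a secondary or sensitivity analysis, because they are self-reported after the outcome.

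The time point must not depend on whether the infant was tested. Suppose the window closed at the week-10 test for tested infants but at week 14 for untested ones. With 25% travelling, trips even over 26 weeks and no true effect, 0.25 × 10/26 = 9.6% of tested and 0.25 × 14/26 = 13.5% of untested infants would be exposed. At 90% completion, apparent completion would be (0.9 × 0.096)/(0.9 × 0.096 + 0.1 × 0.135) = 86.5% in exposed and (0.9 × 0.904)/(0.9 × 0.904 + 0.1 × 0.865) = 90.4% in unexposed infants, a spurious deficit of about 4 points. At 70% completion the same calculation gives about 8 points.

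The cost is a few lines of text and one derived variable from data already collected. The downside is fewer exposed mother-infant pairs, roughly 10-15 of 100 under the even-spread assumption. The result should therefore be reported as an estimate with its confidence interval and described as imprecise.
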